**SECTION 3. Epidemiologic Research Involving Prisoners****Only complete if applicable:**

Effective June 20, 2003, DHHS adopted policy that allows waiver of the requirement for documenting applicability of a category (as found in Section 1 of this form) for certain epidemiologic research involving prisoners. This waiver applies to epidemiologic research on prisoners that presents no more than minimal risk and no more than inconvenience to the prisoner-subjects.

Check this box if your research meets all three criteria listed below, then provide justification in the space provided.

1. I request a waiver for meeting the category conditions under Section 1 of this form.
2. My research involves epidemiologic research intended to describe the prevalence/incidence of a disease by identifying all cases, or to study potential risk factor associations for a disease; **and**
3. Prisoners are not the sole focus of my research.

Justify how the research presents no more than minimal risk and no more than inconvenience to the subjects:

**SECTION 4. Prisoners are not the targeted population****Only complete if applicable:**

Although prisoners may not be the target population for your research, a subject could become a prisoner during the course of the study (particularly if studying a subject population at high-risk of incarceration).

**Note:** If you did not receive IRB approval for involvement of prisoners, and a subject becomes a prisoner during the study, **all research activities involving the now-incarcerated participant must cease** until IRB approval has been issued for their continuation in the research. If you need IRB approval for a prisoner subject to continue participation in your research, select and complete the applicable category from Section 1, complete section 2 and this section, then submit for IRB review.

*In special circumstances where it is in the best interest of the subject to remain in the research study while incarcerated, the IRB Chairperson may determine that the subject may continue to participate in the research prior to satisfying the requirements of Subpart C. However, subsequent IRB review and approval of this completed form is required.*

Prisoners are not a target population for my research, but a subject became a prisoner during the study and I am seeking IRB approval so the subject can continue participation in the research.

Explain the importance of continuing to intervene, interact, or collect identifiable private information during the participant's incarceration:

**SECTION 5. Kentucky (KY) Department of Corrections (DoC) Approval**

Review the following conditions and determine whether any apply to your study:

- active recruitment of participants from a correctional facility (prison, jail, or community corrections institution);
- active recruitment of individuals under community supervision from a state probation and parole office.

If any of the above conditions apply to your research, refer to the [Kentucky Department of Corrections Policy and Procedures, Management Information and Research \(Chapter 5\)](#) for information about submitting a proposal for DoC approval of research including the DoC approved Research Consent and Research Agreement (5.1.G.1).

If your research involves a certificate of confidentiality or the Department of Corrections is directly involved in the study as a sponsor (or otherwise), contact [name], Legal Counsel, at [[contact]](mailto:[contact]), or [contact], for additional information.

**INFORMED CONSENT/ASSENT PROCESS/WAIVER****0 unresolved  
comment(s)**

For creating your informed consent attachment(s), please download the most up-to-date version listed in "All Templates" under the APPLICATION LINKS menu on the left, and edit to match your research project.

Additional Resources:

- [Informed Consent/Assent Website](#)
- [Waiver of Consent vs. Waiver of Signatures](#)
- [Sample Repository/Registry/Bank Consent Template](#)

**Consent/Assent Tips:**

- If you have multiple consent documents, be sure to upload each individually (not all in a combined file).
- If another site is serving as the IRB for the project, attach the form as a "Reliance Consent Form" so the document will not receive a UK IRB approval stamp; the reviewing IRB will need to stamp the consent forms.
- Changes to consent documents (e.g., informed consent form, assent form, cover letter, etc...) should be reflected in a 'tracked changes' version and uploaded separately with the Document Type "Highlighted Changes".
- It is very important that only the documents you wish to have approved by the IRB are attached; DELETE OUTDATED FILES -- previously *approved* versions will still be available in Protocol History.
- Attachments that are assigned a Document Type to which an IRB approval stamp applies will be considered the version(s) to be used for enrolling subjects once IRB approval has been issued.

Document Types that do NOT get an IRB approval stamp are:

- "Highlighted Changes",
- "Phone Script", and
- "Reliance Consent Form",
- "Sponsor's Sample Consent Form".

**How to Get the Section Check Mark**

1. You must:
  - a) provide a response in the text box below describing how investigators will obtain consent/assent, and
  - b) check the box for at least one of the consent items and/or check mark one of the waivers
2. If applicable attach each corresponding document(s) **as a PDF**.
3. If you no longer need a consent document approved (e.g., closed to enrollment), or, the consent document submitted does not need a stamp for enrolling subjects (e.g., umbrella study, or sub-study), only select "Stamped Consent Doc(s) Not Needed".
4. After making your selection(s) be sure to scroll to the bottom of this section and SAVE your work!

Check All That Apply

- Informed Consent Form (and/or Parental Permission Form and/or translated short form)
- Assent Form
- Cover Letter (for survey/questionnaire research)
- Phone Script
- Informed Consent/HIPAA Combined Form
- Debriefing and/or Permission to Use Data Form
- Reliance Consent Form
- Sponsor's sample consent form for Dept. of Health and Human Services (DHHS)-approved protocol
- Stamped Consent Doc(s) Not Needed

**Attachments**

**Informed Consent Process:**

Using active voice, describe how investigators will obtain consent/assent. Include:

- the circumstances under which consent will be sought and obtained

- the timing of the consent process (including any waiting period between providing information and obtaining consent)
- who will seek consent
- how you will minimize the possibility of coercion or undue influence
- the method used for documenting consent
- if applicable, who is authorized to provide permission or consent on behalf of the subject
- if applicable, specific instruments or techniques to assess and confirm potential subjects' understanding of the information

Note: all individuals authorized to obtain informed consent should be designated as such in the E-IRB "Study Personnel" section of this application.

Special considerations may include:

- Obtaining consent/assent for special populations such as children, prisoners, or people with impaired decisional capacity
- *Research Involving Emancipated Individuals*  
If you plan to enroll some or all prospective subjects as emancipated, consult with UK legal counsel **prior to submitting this application to the IRB**. Include research legal counsel's recommendations in the "Additional Information" section as a separate document.
- *Research Involving Non-English Speaking Subjects*  
For information on inclusion of non-English speaking subjects, or subjects from a foreign culture, see IRB Application Instructions for Recruiting Non-English Speaking Participants or Participants from a Foreign Culture.
- *Research Repositories*  
If the purpose of this submission is to establish a research repository describe the informed consent process. For guidance regarding consent issues, process approaches, and sample language see the [Sample Repository/Registry/Bank Consent Template](#).

Aim 1: Potential participants will be read the interview script and will be asked to verbally consent to completing the interview. A waiver of documented informed consent has been requested, because the consent document would be the only link between the research activities and the participant (Option 1) and the main risk would be related to a breach of confidentiality. Participants will be offered the opportunity to sign a stamped consent form if they would prefer.

Aim 2: Potential participants who are interested in the study will be asked to participate in the screening session at the jail with the UK research coordinator (See Research Procedures). Potential participants will be provided with informed consent prior to the screening session. As part of the informed consent process, potential participants will be assured that: (a) Neither participation nor refusal to participate in a protocol will affect their legal parole status (if applicable); (b) No individual or identifiable data collected as part of a study protocol will be made available to any criminal justice authority including jail, parole, or community mandated treatment; and (c) If potential participants do NOT wish to participate, their parole or other legal status will not be affected. Potential participants who choose NOT to participate in the study protocol will not be identified in their records, and non-participation will NOT become a matter of official record in any file. For the focus groups, the consent procedure will only cover the focus group. Focus groups will be audio recorded unless anyone objects. For the pilot trial, informed consent procedures will cover participation in the screening session, medical evaluation, HIV/HCV testing procedures, baseline interview, medication trial, and follow-up interviews so that participants are fully aware of all possible study procedures and possible risks before making a decision about entering the study. A medication guide for Vivitrol will also be given to each participant. Due to the sensitive nature of some of the questions asked in the interviews, confidentiality issues will be stressed during informed consent which will include a description of a federal Certificate of Confidentiality which provides an additional layer of human subject protection. Participants will also be assured that their screening results, study participation, and study data will not be made available to any representative of the criminal justice system. The research coordinator will keep detailed records on the number of interested participants who participate in the screening session and the number of refusals. Screening data will be examined as part of the implementation phase to examine characteristics of participants who enter the study compared to those who are not eligible. Because of the short time frame between baseline and follow-up interview (3 months), consent procedures will not be repeated since no new procedures will be introduced. The Kentucky Department of Corrections (DOC) requires us to provide the DOC with the study title and participant name of individuals under their supervision, including inmates, parolees, or individuals likely to be incarcerated by the DOC.

\*\*Due to COVID-19 restrictions, we are requesting a waiver of documented informed consent (described in detail in the Informed Consent page) for the Screening consent only. Research staff will still review the Screening consent in detail with potential participants over the phone and there will be a section added to the IRB-approved Screening consent document for staff to verify that they reviewed the consent with the participant, answered any questions, that the participant agreed to participate in the study, and the participant's name. The research activities covered in the Screening consent present no more than minimal risk to participant. If the participant qualifies to continue with the study after screening, the research assistant conducting the screening will review the Pilot Trial consent with the participant over the phone. When the Little Flower Clinic staff meet with the participant to conduct the Medical Evaluation session they will first review the Pilot Trial consent with the participant and if the participant agrees to continue they will be asked to sign the Pilot Trial consent form at that time. The Pilot Trial consent to be used during COVID-19 restrictions will contain both the name of the staff obtaining informed consent in person and the staff who reviewed the consent over the phone. We have uploaded new consents to use while the COVID-19 restrictions are in place, which a version indicating where changes have been made compared to the previously approved version. Once COVID-19 restrictions are lifted the previously approved process of documented informed consent will resume.

Participants will be encouraged to call the Principal Investigator if any questions arise during the course of the research. Phone numbers for the PI and the ORI are included in the consent form. It is expected that providing the phone number and contact information for the PI may offer a safe, confidential, and reliable channel for participants to express problems, concerns or questions, and obtain study information since the PI will not, on most occasions, be the person originally collecting the data.

Request for Waiver of Informed Consent Process

If you are requesting IRB approval to waive the requirement for the informed consent process, or to alter some or all of the elements of informed consent, complete, Section 1 and Section 2 below.

Note: The IRB does not approve waiver or alteration of the consent process for greater than minimal risk research, except for planned emergency/acute care research as provided under FDA regulations. Contact ORI for regulations that apply to single emergency use waiver or acute care research waiver [contact]).

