## 17. Supplementals

To ensure the IRB has the most accurate information for your protocol you are expected to re-visit the E-IRB application sections and make corrections or updates as needed. At a minimum you are being asked to review the following sections for accuracy:

- STUDY DRUG INFORMATION—Please review for accuracy.
- STUDY DEVICE INFORMATION—Please review for accuracy.
- RESEARCH ATTRIBUTES—Please review for accuracy.
- OTHER REVIEW COMMITTEES -- Please review for accuracy.

**PROJECT INFORMATION****0 unresolved  
comment(s)**

Title of Project: (Use the exact title listed in the grant/contract application, if applicable).

If your research investigates any aspect of COVID-19, please include "COVID19" at the beginning of your Project Title and Short Title

Re-entry XR-NTX for rural individuals with opioid use disorder

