**Study Population:**

Describe the characteristics of the subject population, including age range, gender, ethnic background and health status. Identify the criteria for inclusion and exclusion.

Provide the following information:

- A description of the subject selection criteria and rationale for selection in terms of the scientific objectives and proposed study design;
- A compelling rationale for proposed exclusion of any sex/gender or racial/ethnic group;
- Justification for the inclusion of vulnerable groups such as children, prisoners, adults with impaired consent capacity, or others who may be vulnerable to coercion or undue influence.

Please consider these resources:

- [NIH Diversity Policy](#)
- [FDA Diversity Guidance](#)

Gender disparities faced by Appalachian individuals call for the critical need for prevention services for this high-risk population. Research indicates that women drug users, in general, are more likely to have injecting intimate partners, and with fewer economic resources to buy drugs, they are more likely to engage in sex exchange to obtain drugs. So, women will be prioritized in this trial. Studies of rural drug users are challenging because recruitment of this high-risk population can be limited by the lack of formal treatment opportunities, travel distances to study sites, and the general protective nature of rural social networks (Friedman, 2003). This study will utilize local rural jails as venues for screening and recruitment of high-risk drug users, followed by targeted prevention efforts in the community post-release. For Aim 1, the study population will include stakeholders (n=10) who are community health/behavioral health providers and community supervision officers. Aim 1 will also include participants (n=20) in focus groups who mirror the pilot trial inclusion/exclusion criteria. The second set of interviews will include key stakeholders who work in community supervision and health care providers (n=15) and individuals who have used opioids and are incarcerated or on community supervision (n=15). For Aim 2, the pilot trial will include participants who are incarcerated at the time of study recruitment or currently on community supervision in Perry County, KY (n=60). Based on pre-screening and medical evaluation, inclusion and exclusion criteria is described below, and summarized in the attached Research Strategy:

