***b) Describe what measures will be taken to prevent intervention by prison authorities in the selection process:***

Consistent with our current R01 (IRB protocol #12-0372), while jail staff may monitor participant entry and exit into the visitation room for the screening, medical evaluation, and interview process, no jail staff will be present for any study related procedures.

**Condition 4.** Parole boards cannot take into consideration a prisoner's participation in research. Informed consent must state participation will not impact parole.

***Describe what measures are in place to ensure parole boards are not influenced by prisoners' participation in research and how prisoners will be told their participation (or refusal or withdrawal from) will not impact parole:***

Based on our current study, we anticipate that most of our participants will be on probation rather than parole. However, confidentiality issues will be stressed during informed consent and will include the description of a federal Certificate of Confidentiality. Participants will also be assured that their screening results, HIV/HCV test results, study participation, and study data will not be made available to any representative of the jail or criminal justice system. Jail officials and administrators will not be informed of participants who participate in the screening, eligibility data, or refusals in order to protect participant confidentiality. Consent form language reflects this emphasis on participant confidentiality.

**Condition 5.** For studies that require follow-up, provisions are made including consideration for the length of individual sentences; informed consent must reflect provisions for follow-up.

***Describe what provisions have been made for follow-up and how this information will be relayed to the prisoner participants:***

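### The consent plan assures participants that their study participation will not reach the criminal justice system, yet says the Kentucky Department of Corrections must be given the names of those it supervises

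*Protocol*

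**What the plan says.** Three statements in the protocol bear on the point.

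- **Informed Consent Process, Aim 2, the assurance.** Participants are to be told that "their screening results, study participation, and study data will not be made available to any representative of the criminal justice system". Participation is listed as an item of its own, apart from screening results and study data. Assurance (b), earlier in the same paragraph, is narrower: "No individual or identifiable data collected as part of a study protocol will be made available to any criminal justice authority".
- **Prisoners, Section 2, Condition 4.** The answer on keeping parole decisions independent of the research repeats the promise and again names participation: "study participation, and study data will not be made available to any representative of the jail or criminal justice system".
- **Informed Consent Process, Aim 2, last sentence.** The Kentucky DOC "requires us to provide the DOC with the study title and participant name of individuals under their supervision", with the reach of the requirement given as "including inmates, parolees, or individuals likely to be incarcerated by the DOC".

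The Study Population section draws the 60 planned Aim 2 participants from people in jail or on community supervision in Perry County. The title in Project Information is "Re-entry XR-NTX for rural individuals with opioid use disorder".

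**The concern.** The assurance has no exception, and the reporting requirement does not refer back to it. People in custody or on supervision have a particular interest in whether the corrections agency learns that they joined a study. The title also names the disorder under study, so a report of name and title would tell the agency more than that someone volunteered for research. If the plan were followed as written, staff would give an assurance that the same paragraph contradicts for participants under DOC supervision. What is at stake is the accuracy of what people are told at consent. No endpoint, sample size or analysis depends on it.

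**Working it through.** No statistical figure is involved. The check sets the statements side by side and then bounds the number of people concerned.

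**Step 1: what the assurance covers.** It has three objects: screening results, participation and study data. Because participation is listed separately, the assurance cannot be read as a promise about collected data alone.

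**Step 2: what the DOC requirement discloses.** A person's name paired with the study's title states that this person is in this study. That is the second object of the assurance. The requirement mentions neither of the other two.

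**Step 3: whether the DOC falls inside the promise.** The confidentiality text treats DOC personnel as including jail staff and probation and parole officers. On the document's own usage, then, the DOC is part of the criminal justice system. No text shown makes it an exception.

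**Step 4: result for each object.**

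| Object | Promised not to go to the criminal justice system | Stated to go to the DOC | Conflict |
|---|---|---|---|
| Identity and participation | Yes | Yes, for those it supervises | Yes |
| Screening and test results | Yes | Not stated | None shown |
| Interview and other study data | Yes | Not stated | None shown |

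Assurance (b) concerns data collected under the protocol. It conflicts only if a reported name counts as such data, which the text does not settle, so the point does not rest on it.

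**Step 5: how many people.** From Continuation Review items 5 (Subject Info To-Date) and 14 (Subject Demographics):

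- Aim 2 to date: 9 with a baseline + 13 without = 22.
- Check against total enrolment: 10 in Aim 1 + 22 = 32, and item 5 gives 23 + 9 = 32.
- Check against the demographic table: 14 + 5 = 19 known = 10 + 9, and 19 + 13 = 32.

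The ceiling is therefore 22 if names are reported from screening onward, and 9 if only baseline completers are reported. The floor is 0, because the protocol does not give the reporting point, the number under DOC supervision, or whether any report was made.

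**The case against.** The strongest reply is that the consent forms are not shown and may already disclose the report. There is some support for this. The DOC sentence sits in the answer describing the consent process. The confidentiality section says the form already has a statement on access to state offender records. The section on DoC approval refers applicants to "DoC approval of research including the DoC approved Research Consent and Research Agreement", although that is template wording and weak evidence about this study. This stands as far as harm is concerned: nobody can be said to have been misinformed. It does not remove the conflict, because the assurance that staff are told to give would still contradict a form that discloses the report.

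A second reply is that the study is nearly over. Item 8 of the Continuation Review limits remaining work to data analysis, so new wording may reach no new participant. This is also fair, and it makes the check of the forms more useful than the rewording.

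A third is that the obvious repair, deleting participation from the promise, would weaken the Condition 4 answer, whose purpose is to protect prisoners. This stands too. The protocol does not say which statement should give way. The DoC approval section sends studies with a Certificate of Confidentiality to legal counsel, and the confidentiality section says a certificate has been obtained.

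Finally, Condition 4 is the weaker of the two places. Its answer does not name Aim 2, although the screening and HIV/HCV results it lists are pilot-trial procedures. Its specific promise that jail officials and administrators will not be informed of who is screened is not contradicted by a report to the DOC as such. Only its general sentence conflicts.

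**Conclusion.** The conflict is real and worth fixing. For a participant under DOC supervision, the promise about participation and the name-and-title requirement cannot both hold. This follows from the wording alone and assumes only that the DOC belongs to the criminal justice system, as the protocol's own usage implies.

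A reader might infer more, and the protocol does not support it:

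- That study data reach the DOC: the requirement covers name and title only.
- That individual officers see the report, or that names have already been sent: neither is stated.
- That participants were misled: this depends on forms not shown.
- That all or most of the 60 planned are affected: the number under DOC supervision is not given, and enrolment to date in Aim 2 is 22.

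The size is therefore 0 to 22 people. Confidence is high for the contradiction in the text and low for any consequence.

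**What to change.** 1. Settle whether names must be sent, using the legal counsel contact that the Prisoners section on DoC approval gives for studies with a Certificate of Confidentiality.
2. If names are sent, keep the assurance and add an explicit exception in both the Informed Consent Process and the Condition 4 answer. It should say that the DOC receives the name and the study title for people under its supervision, and at what point. Keep the statement that taking part will not affect parole, which Condition 4 requires.
3. If names are not sent, remove the DOC sentence.
4. Check that the screening and pilot-trial consent forms match the outcome. Screening consent could be verbal under the COVID-19 waiver, so for people screened by phone the signed pilot-trial form is the one that can document the disclosure.
5. Only if names were sent and the forms were silent, notify the affected Aim 2 participants.

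The cost is one legal query, a few sentences in two places and a check of two forms. The conditional notice would go to at most 22 people on present enrolment.
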